3.3 Study Oversight for Safety Evaluation

A subject may elect to discontinue study drug at any time for safety, medical, or personal reasons. Patients who choose to discontinue study drug prior to disease progression will be followed in the post study treatment follow up period and continue to undergo regularly scheduled disease assessment until documentation of disease progression or start of an alternative anticancer treatment. All subjects who discontinue study drug will be followed for overall survival and all post progression cancer treatments administered will be recorded. Subjects may at any time withdraw consent for further study participation. No further data will be collected on subjects once consent has been withdrawn. The investigator will promptly explain to the subject involved that the study drug will be discontinued for that subject and provide appropriate medical treatment and other necessary measures for the subject. A subject who has ceased to return for visits will be followed up by mail, phone, or other means as much as possible to gather information such as the reason for failure to return and the status of treatment compliance, presence or absence of adverse events, and clinical courses of signs and symptoms, and the information will be recorded in the CRF.

Subjects who discontinue early from the study or treatment will be discontinued for 1 of these primary reasons: adverse event(s), lost to follow-up, subject choice, progressive disease, or administrative/other. In addition to the primary reason, the subject may have indicated 1 or more of these reasons as secondary reasons for discontinuation. Study disposition information will be collected on the appropriate CRF. A subject removed from the study for any reason may not be replaced.

Safety will be assessed by monitoring and recording all AEs including all CTCAE grades (for both increasing and decreasing severity) and serious adverse events (SAEs); regular monitoring of hematology, clinical chemistry, and urine values; physical examinations; and regular measurement of vital signs, and electrocardiograms (ECGs) as detailed in the schedule of visits and procedures.

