4.3 Withdrawal of Subjects from Study Treatment and/or Study

Permanent discontinuation of investigational product/study treatment

An individual subject will not receive any further investigational product if any of the following occur in the subject in question:

1. Withdrawal of consent or lost to follow-up.
2. Adverse event that, in the opinion of the investigator or the sponsor, contraindicates further dosing.
3. Subject is determined to have met one or more of the exclusion criteria for study participation at study entry and continuing investigational therapy might constitute a safety risk.
4. Pregnancy or intent to become pregnant.
5. Any AE that meets criteria for discontinuation as defined in Section 10.3.
6. Grade ≥ 3 infusion reaction.
7. Subject noncompliance that, in the opinion of the investigator or sponsor, warrants withdrawal; eg, refusal to adhere to scheduled visits.
8. Initiation of alternative anticancer therapy including another investigational agent.
9. Confirmed PD by RECIST 1.1 (CT scan or MRI at 4-6 weeks that confirms progression) and investigator determination that the subject is no longer benefiting from treatment with durvalumab + tremelimumab. Patients with documented tumor progression by image (all time-points but especially at 12 weeks), the progression should be confirmed with an additional imaging test (same characteristics) within 4-6 weeks. Treatment should continue according to protocol, until disease progression is confirmed, according the aforementioned procedure.
10. No restarts are allowed after a delay of more than 12 weeks due to toxicity or more than 4 weeks of delay if **the reason is different from toxicity** without consulting the Coordinating Investigator.

Subjects who are permanently discontinued from further receipt of investigational product, regardless of the reason (withdrawal of consent, due to an AE, other), will be identified as having permanently discontinued treatment.

Subjects who are permanently discontinued from receiving investigational product will be followed for safety per Section 10.0 and Appendix 1 or 2, including the collection of any protocol-specified blood specimens, unless consent is withdrawn or the subject is lost to follow-up or enrolled in another clinical study. All subjects will be followed for survival. Subjects who decline to return to the site for evaluations will be offered follow-up by phone every **3 months as an alternative**.

Withdrawal of consent

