8.1.3 End of Treatment

End of treatment is defined as the last planned dosing visit within the 12-month dosing period. For subjects who discontinue durvalumab or tremelimumab prior to 12 months, end of treatment is considered the last visit where the decision is made to discontinue treatment. All required procedures may be completed within \pm 7 days of the end of treatment visit. Repeat disease assessment is not required if performed within 28 days prior to the end of treatment visit.

Blood samples for biomarker analysis are collected.

Assessments for subjects who have completed durvalumab and tremelimumab treatment and achieved disease control, or have discontinued durvalumab or tremelimumab due to toxicity in the absence of confirmed progressive disease are provided in APPENDIX 2.

Assessments for subjects who have discontinued durvalumab or tremelimumab treatment due to

Clinical Study Protocol
 Drug Substance DURVALUMAB/TREMELIMUMAB
 Study Number ESR 15-11561-61-DUNE
 EudraCT Nº: 2016-002858-20
 Edition Number: 5.0 dated on June 09th, 2021

confirmed PD are presented in APPENDIX 3.

All subjects will be followed for survival until the end of the study regardless of further treatments, or until the sponsor ends the study.

Follow-up period

TC/MRI every 12 weeks until progression. Monthly visits during the first 3 months after end of treatment, every 2 months until one year, and therefore every 6 months. Determinations to be done are listed in appendix 2 and 3.

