9. DISEASE EVALUATION AND METHODS

Primary Objective

Disease evaluation according RECIST 1.1.

A copy of the RECIST 1.1 guideline will be included in the ISF.

RECIST 1.1 will be modified so that PD must be confirmed at the next scheduled visit, preferably, and no earlier than 4 weeks after the initial assessment of PD in the absence of clinically significant deterioration. Treatment with durvalumab + tremelimumab would continue between the initial assessment of progression and confirmation for progression.

Secondary objectives (irRECIST)

The response to immunotherapy may differ from the typical responses observed with cytotoxic chemotherapy including the following (Wolchok et al 2009, Nishino et al 2013):

- Response to immunotherapy may be delayed
- Response to immunotherapy may occur after PD by conventional criteria
- The appearance of new lesions may not represent PD with immunotherapy
- SD while on immunotherapy may be durable and represent clinical benefit.

Based on the above-described unique response to immunotherapy and based on guidelines from regulatory agencies, e.g., European Medicines Agency's "Guideline on the evaluation of anti-cancer medicinal products in man" (EMA/CHMP/205/95/Rev.4) for immune modulating anti-cancer compounds, the study may wish to implement the following in addition to standard RECIST 1.1 criteria:

- RECIST 1.1 will be modified so that PD must be confirmed at the next scheduled visit, preferably, and no earlier than 4 weeks after the initial assessment of PD in the absence of clinically significant deterioration. Treatment with durvalumab + tremelimumab would continue between the initial assessment of progression and confirmation for progression.
- In addition, subjects may continue to receive durvalumab + tremelimumab beyond confirmed PD in the absence of clinically significant deterioration and if investigators consider that subjects continue to receive benefit from treatment.

Progression would be considered confirmed if the following criteria are met:

- ≥20% increase in the sum diameters of target lesions compared with the nadir at 2 consecutive visits with an absolute increase of 5 mm, and/or
- Clinically significant progression (worsening) of non-target lesions or new lesions at the confirmatory PD time point compared with the first time point where progression of non-target lesions or new lesions was identified, and/or

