10.3.2.1 Reporting of deaths

All deaths that occur during the study, or within the protocol-defined 90-day post-last dose of durvalumab + tremelimumab safety follow-up period must be reported as follows:

- Death that is clearly the result of disease progression should be documented but should not be reported as an SAE.
- Where death is not due (or not clearly due) to progression of the disease under study, the AE causing the death must be reported to as a SAE within **24 hours** (see Section 10.3.2 for further details). The report should contain a comment regarding the co-involvement of progression of disease, if appropriate, and should assign main and contributory causes of death.
- Deaths with an unknown cause should always be reported as a SAE.

Deaths that occur following the protocol-defined 90-day post-last-dose of durvalumab safety follow-up period will be documented as events for survival analysis, but will not be reported as an SAE.

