11.2. Methods of statistical analyses

Strategic decisions about future development of immune therapy in neuroendocrine tumors will be available after the results of this trial.

Summary tables (descriptive statistics and frequency tables) will be provided for all baseline variables, efficacy variables, and safety variables, as appropriate. Continuous variables will be summarized with descriptive statistics (mean, standard deviation, range, and median). Ninety-five (95) percent confidence intervals (95% CI) may also be presented, as appropriate. Frequency counts and percentage of subjects within each category will be provided for categorical data.

The primary efficacy analysis will be performed using the binomial test procedure. Missing data will be treated using statistical multiple random imputation.

Secondary endpoints will be summarized with descriptive statistics. Continuous variables will be summarized with n, mean, standard deviation, and range, frequency counts and percentage of subjects within each category will be provided for categorical data. Multivariate regression models will be used to study relations between explanatory variables and primary endpoint. Survival analysis will be performed to analyze PFS, Kaplan-Meier curves will be presented and possible comparisons will be tested using the log-rank test or the Cox proportional hazard model for multivariate analysis, hazard ratios (HR) and their 95% confidence interval (CI95%) will be provided. Patients with lost of follow-up or treatment discontinuation will be included in the final analysis of primary endpoint if they have at least one tumor evaluation and considered as censored data for survival endpoints.

R software version 3.2.1 will be used for all analysis.

Safety Analyses

Safety analyses will be based on the Safety Analysis Set. All safety analyses will be summarized separately by cohort. Adverse events and serious adverse events, laboratory test results, physical examination findings and vital signs, and their changes from baseline will be summarized using descriptive statistics. Abnormal values will be flagged.

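### The plan censors patients for stopping treatment, which read literally contradicts its rule that later deaths are survival events; the PFS event is undefined and duration of response is summarised without censoring

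*Protocol*

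**What the plan says.** **The censoring sentence.** Protocol 11.2 groups loss to follow-up with treatment discontinuation. Such patients enter the primary analysis if they have at least one tumour evaluation, and they are "considered as censored data for survival endpoints". The same sentence stands in the synopsis and in SAP 3.7.3. None of the three gives a censoring date or exempts any reason for stopping.

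**Deaths after treatment.** Protocol 10.3.2.1 says that deaths later than 90 days after the last dose "will be documented as events for survival analysis".

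**Survival follow-up.** Protocol 3.3: "All subjects who discontinue study drug will be followed for overall survival". Protocol 4.3: "All subjects will be followed for survival". Protocol 8.1.3, repeated in SAP 3.4: "All subjects will be followed for survival until the end of the study regardless of further treatments". SAP Tables 110 and 111 have a column for the number of deaths, without restriction.

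**PFS.** Median PFS by irRECIST is a secondary objective (Protocol 2.2), but no section defines the event. SAP Tables 108 and 109 have a column for the number of progressions and none for deaths.

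**Duration of response.** SAP Tables 101 and 103 ask for n, mean (SD), median (IQR), range and a confidence interval for the mean. Protocol 11.2 and SAP 3.7.3 name only PFS for Kaplan-Meier analysis.

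**The concern.** A patient who stops treatment and later dies is, on the literal rule, not a death in the overall survival analysis. Stopping is closely tied to prognosis, especially in cohort 4, so this is informative censoring. It pushes the Kaplan-Meier curve upward whenever the hazard of death is higher after stopping than on treatment.

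The PFS and duration-of-response gaps add to this. Two analysts could produce different secondary results from the same data and both claim to follow the plan. With 31 to 33 patients per cohort and no control arm, these estimates will be read against outside data, so their definitions matter.

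**Working it through.** **1. Can the passages be applied together?** A death more than 90 days after the last dose occurs in someone who has stopped treatment. Protocol 10.3.2.1 makes it a survival event; the literal sentence in 11.2 makes that patient censored. Both cannot be applied. The sections on survival follow-up govern data collection, so they do not strictly contradict a censoring rule; the rule simply leaves their data unused.

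**2. Overall survival, cohort 4, literal rule with censoring at the stop.** The documents give only the 13% 9-month reference and the 23% expected rate (Protocol 11.3). Assumed: exponential time on treatment with median 2 months, so exit hazard L = ln 2 / 2 = 0.347 per month; a share f = 10/20/40% of exits are deaths; the other patients stop and then die at hazard m.

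- True survival: S(t) = exp(-Lt) + (1-f)·L·[exp(-mt) - exp(-Lt)]/(L-m).
- Solving S(9) = 0.13 gives m = 0.434/0.405/0.338. Solving S(9) = 0.23 gives m = 0.262/0.239/0.186.
- Under the rule, Kaplan-Meier estimates exp(-fLt).

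| 6-month overall survival | f=10% | f=20% | f=40% |
|---|---|---|---|
| True, 9-month rate 13% | 31% | 30% | 28% |
| True, 9-month rate 23% | 43% | 42% | 39% |
| Under the rule | 81% | 66% | 44% |

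**3. What can be said about the median.** The formula gives 2/f = 20/10/5 months, against a true 4.1/4.0/3.7 months (9-month rate 13%) or 5.2/5.0/4.5 months (23%). But planned treatment ends at about 12 months (Protocol 3.1 and 3.2). Ignoring retreatment, nobody stays at risk beyond that. With 33 patients, 33·exp(-6L) = 4.1 are at risk at 6 months and 33·exp(-12L) = 0.5 at 12 months. Simulating 33 patients with a 12-month cap, the median is reached in about 18% of trials for f = 10% and 49% for f = 20%. The likely result there is a median that cannot be estimated.

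**4. PFS, the censoring sentence.** Protocol 4.3 says "Treatment should continue according to protocol, until disease progression is confirmed", and Protocol 9 adds that "subjects may continue to receive durvalumab + tremelimumab beyond confirmed PD". Progression is therefore normally recorded before the stop, and censoring at the stop mainly touches patients who stop for an adverse event (about 15%, Protocol 1.4.2.3). Let h be the event hazard on treatment, a the adverse-event stopping hazard (15% stopping within 13 months), and rh the event hazard afterwards. Then S(t) = exp(-(a+h)t) + a·[exp(-rht) - exp(-(a+h)t)]/(a+h-rh), and the rule gives exp(-ht). With a 9-month rate of 30% and r = 0.5/1/2 (assumed), h = 0.144/0.134/0.124. Twelve-month PFS moves from 21.0/20.1/19.6% to 17.7/20.1/22.6%.

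**5. PFS, deaths without progression.** If they were not counted and made up a share q of first events, PFS would read S(t)^(1-q) under exponential times. For a 9-month rate of 30%, 6-month PFS is 0.30^(6/9) = 44.8%; it would read 46.6/48.6/52.6% for q = 5/10/20% (assumed).

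**6. Duration of response.** Assumed: exponential durations with median 12/18/24 months (means 17.3/26.0/34.6), response at the first 12-week scan (2.8 months), uniform accrual. Protocol 13.6 (first patient April 2017, last patient December 2019, last visit December 2021) then gives 21.2 to 53.2 months of follow-up after response. The SAP 3.8.1 timetable gives 9.2 to 33.2 months.

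| Handling of ongoing responses | Mean | Median |
|---|---|---|
| Treated as finished, protocol timetable | 15.0/19.4/22.4 | 12.0/18.0/22.5 |
| Left out, protocol timetable | 12.3/14.4/15.6 | 9.8/12.1/13.5 |
| Treated as finished, SAP timetable | 11.8/14.1/15.5 | 10.8/13.2/14.8 |

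**The case against.** The best defence is that the sentence is loosely worded and means only that patients who are event-free at last contact are censored there. Protocol 10.3.2.1 and the unrestricted death column in Tables 110 and 111 fit that reading, and it removes the conflict. This stands as a plausible intention. It does not settle the matter: the sentence puts discontinuation on the same footing as loss to follow-up, and the SAP, to which Protocol 11.1 defers for detail, repeats it unchanged.

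It is also fair that the size in step 2 rests on assumed exit rates, and that the affected analyses are secondary or exploratory.

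Several stronger inferences are tempting and not supported:

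- **That the cohort 4 primary result is biased.** It is a binomial proportion alive at 9 months, and the same sentence deals with the primary endpoint separately. It is affected only if the censoring is carried over.
- **That a 20-month median would be reported.** Step 3 shows that this extrapolates beyond any follow-up under the rule.
- **That the plan excludes deaths from PFS.** A column label in an empty table does not say whether such a death is an event, censored or competing.
- **That censoring at the stop seriously biases PFS.** The shift in step 4 is about -3 to +3 points, with no fixed sign.
- **That duration-of-response medians are always too short.** With long follow-up and ongoing responses treated as finished, they are nearly right.

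**Conclusion.** The point holds as a defect of wording and of table design. Read literally, the censoring sentence contradicts Protocol 10.3.2.1 and makes overall survival informatively censored. Under the step 2 assumptions with 9-month survival at 13%, the 6-month rate is overstated by roughly 16 to 50 percentage points (44 against 28; 81 against 31), and the median would often not be estimable. The upward direction depends on a higher death hazard after stopping than on treatment, which holds in every case shown.

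The PFS event is undefined; if deaths without progression were not counted, PFS would be biased upward. Mean duration of response is too low whenever responses are ongoing; its median is too short if ongoing responses are left out.

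Confidence is high that the definitions are missing or in conflict. It is lower for the sizes, which depend on inputs that the documents do not give. This should be fixed before the secondary analyses are run.

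**What to change.** Replace the sentence in Protocol 11.2, the synopsis and SAP 3.7.3 with explicit definitions:

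- **Overall survival:** event is death from any cause; censor at the last date known alive, regardless of treatment status.
- **PFS:** event is progression or death from any cause; censor at the last evaluable tumour assessment, with no censoring for stopping study treatment alone. Relabel the event columns of Tables 108 and 109 as progression or death. State how new anticancer therapy is handled in the analysis. Protocol 3.3 runs scans "until documentation of disease progression or start of an alternative anticancer treatment", and 11.1 likewise ends them at new therapy, while 8.1.3 and Appendix 2 continue them to progression; these passages must be reconciled.
- **Duration of response:** Kaplan-Meier among responders, from first response to progression or death, ongoing responses censored, median with 95% confidence interval, in place of the mean-based summary in Tables 101 and 103.

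The cost is wording and table shells. Survival date and status are already collected (SAP 3.5), and PFS and duration of response use scans already planned; how far those extend after new therapy depends on the reconciliation above.

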11.3. Determination of sample size

Sample size has been calculated using one-sample Superiority test (function One Sample Proportion. NIS of the Trial Size package of R software). According to previous knowledge, it is

Clinical Study Protocol
Drug Substance DURVALUMAB/TREMELIMUMAB
Study Number ESR 15-11561-61-DUNE
EudraCT N°: 2016-002858-20
Edition Number: 5.0 dated on June 09th, 2021

estimated that the reference value for the likelihood to be progression-free at 9 months is 30% and we expect an increase of 20% with a superiority margin of 10%. With a unilateral alpha level of 5% and 80% power, we estimate to include 28 patients per group, with an expected lost to follow-up rate of 10%, a final sample size in each 1, 2 and 3 cohort will include 31 patients.

For cohort 4, and according to previous knowledge, it is estimated that the reference proportion of patients being alive at 9 months is 13% and we expect an increase of 10% with a superiority margin of 5%. With a unilateral alpha level of 5% and 80% power, we estimate to include 30 patients per group, with an expected lost to follow-up rate of 10%, a final sample size will include 33 patients. Summarizing, total sample size will include 126 patients: 31 patients for cohorts 1 to 3, and 33 patients for cohort 4.

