Secondary endpoints will be summarized with descriptive statistics. Continuous variables will be summarized with n, mean, standard deviation, and range, frequency counts and percentage of subjects within each category will be provided for categorical data. Multivariate regression models will be used to study relations between explanatory variables and primary endpoint. Survival analysis will be performed to analyze PFS, Kaplan-Meier curves will be presented and possible comparisons will be tested using the log-rank test or the Cox proportional hazard model for multivariate analysis, hazard ratios (HR) and their 95% confidence interval (CI95%) will be provided. Patients with lost of follow-up or treatment discontinuation will be included in the final analysis of primary endpoint if they have at least one tumor evaluation and considered as censored data for survival endpoints.

R software version 3.2.1 will be used for all analysis.

Sample Size Determination:

Sample size has been calculated using one-sample Superiority test (function One Sample Proportion. (NIS) of the Trial Size package of R software). According to previous knowledge, it is estimated that the reference value for the likelihood to be progression-free at 9 months is 30% and we expect an increase of 20% with a superiority margin of 10%. With a unilateral alpha level of 5% and 80% power, we estimate to include 28 patients per group, with an expected lost to follow-up rate of 10%, a final sample size in each 1, 2 and 3 cohort will include 31 patients.

For cohort 4, and according to previous knowledge, it is estimated that the reference proportion of patients being alive at 9 months is 13% and we expect an increase of 10% with a superiority margin of 5%. With a unilateral alpha level of 5% and 80% power, we estimate to include 30 patients per group, with an expected lost to follow-up rate of 10%, a final sample size will include 33 patients.

Summarizing, total sample size will include 126 patients: 31 patients for cohorts 1 to 3, and 33 for cohort 4.

Clinical Study Protocol
Drug Substance DURVALUMAB/TREMELIMUMAB
Study Number ESR 15-11561-61-DUNE
EudraCT Nº: 2016-002858-20
Edition Number: 5.0 dated on June 09th, 2021

Clinical Study Protocol
 Drug Substance DURVALUMAB/TREMELIMUMAB
 Study Number ESR 15-11561-61-DUNE
 EudraCT N°: 2016-002858-20
 Edition Number: 5.0 dated on June 09th, 2021

SCHEDULE OF STUDY ASSESSMENTS (according to section 8)

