6.1.2 Procedures for handling subjects incorrectly enrolled

Patients incorrectly enrolled in the trial will be considered as protocol deviations. If investigator considerer that the patient is obtaining benefit of the investigational treatment, patients could continue on therapy. They will not be considered for the primary endpoint of the trial, neither for efficacy nor biomarker secondary and exploratory analyses. Patients incorrectly enrolled that continue on treatment can be assessed for safety profile endpoint.

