3.6 SAMPLE SIZE

Sample size has been calculated using one-sample Superiority test (function OneSampleProportion. (NIS) of the Trial Size package of R software). According to previous knowledge, it is estimated that the reference value for the likelihood to be progression-free at 9 months is 30% and we expect an increase of 20% with a superiority margin of 10%. With a unilateral alpha level of 5% and 80% power, we estimate to include 28 patients per group, with an expected lost to follow-up rate of 10%, a final sample size in each 1, 2 and 3 cohort will include 31 patients.

For cohort 4, and according to previous knowledge, it is estimated that the reference proportion of patients being alive at 9 months is 13% and we expect an increase of 10% with a superiority margin of 5%. With a unilateral alpha level of 5% and 80% power, we estimate to include 30 patients per group, with an expected lost to follow-up rate of 10%, a final sample size will include 33 patients.

Summarizing, total sample size will include 126 patients: 31 patients for cohorts 1 to 3, and 33 for cohort 4.

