3.7.3 Planned Method of Analysis

Summary tables (descriptive statistics and frequency tables) will be provided for all baseline variables, efficacy variables, and safety variables, as appropriate. Continuous variables will be summarized with descriptive statistics (mean, standard deviation, range, and median). Ninety-five (95) percent confidence intervals (95% CI) may also be presented, as appropriate. Frequency counts and percentage of subjects within each category will be provided for categorical data.

The primary efficacy analysis will be performed using the binomial test procedure. Missing data will be treated using statistical multiple random imputation.

Concordance between investigator assessment and independent central radiology review will be analyzed using Cohen's Kappa. Although no significant differences are expected, a sensitivity analysis for the primary efficacy analysis will be performed using as response variable independent central radiology assessment.

Secondary endpoints will be summarized with descriptive statistics. Continuous variables will be summarized with n, mean, standard deviation, and range, frequency counts and percentage of subjects within each category will be provided for categorical data. Multivariate regression models will be used to study relations between explanatory variables and primary endpoint. Survival analysis will be performed to analyze PFS, Kaplan-Meier curves will be presented and possible comparisons will be tested using the log-rank test or the Cox proportional hazard model for multivariate analysis, hazard ratios (HR) and their 95% confidence interval (CI95%) will be provided. Patients with lost of follow-up or treatment discontinuation will be included in the final analysis of primary endpoint if they have at least one tumor evaluation and considered as censored data for survival endpoints.

R software version 3.2.1 will be used for all analysis.

Safety Analyses

Safety analyses will be based on the Safety Analysis Set. All safety analyses will be summarized separately by cohort. Adverse events and serious adverse events, laboratory test results, physical examination findings and vital signs, and their changes from baseline will be summarized using descriptive statistics. Abnormal values will be flagged.

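### The planned 28 and 30 patients do not give 80% power under the stated superiority inputs, and the null proportion for the binomial test is never stated

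*Protocol*

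**What the plan says.** Protocol 11.3 describes a one-sample superiority calculation made with a named R function. The synopsis and SAP 3.6 repeat it with the same inputs.

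- **Cohorts 1-3** (clinical benefit at nine months): the reference rate is 30%, and the synopsis adds "we expect an increase of 20% with a superiority margin of 10" per cent. The result is "With a unilateral alpha level of 5% and 80% power, we estimate to include 28 patients per group", raised to 31 for 10% loss.
- **Cohort 4** (alive at nine months): "it is estimated that the reference proportion of patients being alive at 9 months is 13% and we expect an increase of 10" per cent. SAP 3.6 gives the margin: "we expect an increase of 10% with a superiority margin of 5" per cent. With the same alpha and power this yields 30, raised to 33.

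For the analysis, SAP 3.7.3 says only "The primary efficacy analysis will be performed using the binomial test procedure", and Protocol 11.2 agrees. Neither document gives a null proportion, a critical count or a success rule. Protocol 11.2 also says: "Strategic decisions about future development of immune therapy in neuroendocrine tumors will be available after the results of this trial".

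**The concern.** A superiority margin normally moves the null up from the reference rate, here to 40% and 18%, which leaves only 10 and 5 points to detect. Samples of 28 and 30 look far too small for that. They also look small if the margin is dropped and the nulls are 30% and 13%.

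Two things are at stake. The first is how a negative cohort is read. A reader who trusts the stated 80% will take a non-significant result as fair evidence against the hoped-for rate, and in cohort 4 in particular it would be nothing of the kind. The second is the success threshold. With the null unstated, the bar can be set at either of two places after the data are seen.

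**Working it through.** **Inputs** (Protocol 11.3, SAP 3.6). Cohorts 1-3: reference 0.30, expected 0.50, margin 0.10. Cohort 4: reference 0.13, expected 0.23, margin 0.05. One-sided alpha 0.05, power 0.80.

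**Step 1: the plan's own figures.** The inflation reproduces: 28 × 1.10 = 30.8, so 31, and 30 × 1.10 = 33. The 28 and 30 do not. The documents name the R function but do not print its formula, so I assume the usual normal approximation, n = (z_α + z_β)² p(1−p)/d², with (1.645 + 0.842)² ≈ 6.18. I also tried the form that uses separate variances under the null and the alternative.

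| How the margin is used | d, cohorts 1-3 / cohort 4 | p at expected rate | p at reference rate | Null/alternative variance |
|---|---|---|---|---|
| Subtracted (null 40% / 18%) | 0.10 / 0.05 | 154.6 / 438.0 | 129.8 / 279.7 | 150.5 / 389.0 |
| Ignored (null 30% / 13%) | 0.20 / 0.10 | 38.6 / 109.5 | 32.5 / 69.9 | 34.5 / 82.3 |
| Added (or reversed: null 20% / 8%) | 0.30 / 0.15 | 17.2 / 48.7 | 14.4 / 31.1 | 12.9 / 28.5 |

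For example, 6.18 × 0.25/0.10² ≈ 155 and 6.18 × 0.1771/0.05² ≈ 438. The only entries near a stated figure are 31.1 and 28.5 for cohort 4. They need the margin to work in the opposite direction from superiority, and on that row cohorts 1-3 come out at 13 to 17, not 28.

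**Step 2: exact power of the named test.** This does not depend on the R function. Take the smallest count r with P(X ≥ r | n, null) ≤ 0.05, then compute P(X ≥ r) at the expected rate.

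| Cohort, true rate | Null | n | r | Attained size | Power |
|---|---|---|---|---|---|
| 1-3, 50% | 30% | 28 | 13 | 4.9% | 71.4% |
| 1-3, 50% | 30% | 31 | 15 | 2.4% | 64.0% |
| 1-3, 50% | 40% | 28 | 16 | 5.0% | 28.6% |
| 1-3, 50% | 40% | 31 | 18 | 3.2% | 23.7% |
| 4, 23% | 13% | 30 | 8 | 3.4% | 38.3% |
| 4, 23% | 13% | 33 | 9 | 2.2% | 34.2% |
| 4, 23% | 18% | 30 | 10 | 3.2% | 13.1% |
| 4, 23% | 18% | 33 | 11 | 2.5% | 11.7% |

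The sizes in between do not reach 80% either. At 29 and 30 the power is 64.5% and 70.8% (null 30%) or 22.9% and 29.2% (null 40%). At 31 and 32 it is 42.3% and 46.1% (null 13%) or 15.6% and 18.2% (null 18%).

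**Step 3: what 80% would take.** The first n at which exact power reaches 80% is 39 (30% vs 50%), 158 (40% vs 50%), 91 (13% vs 23%) and 403 (18% vs 23%). At the enrolled sizes, 80% power needs a true rate of about 54.3% (null 30%) or 63.7% (null 40%) at n = 31, and about 33% (null 13%) or 39% (null 18%) at n = 33.

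**Step 4: the bar in cohort 4.** With 33 patients and a null of 13%, the smallest significant result is 9/33 = 27.3%, above the 23% the cohort was meant to detect.

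**Step 5: the analysed n is not fixed.** Patients lost or discontinued "will be included in the final analysis of primary endpoint if they have at least one tumor evaluation". Of incorrectly enrolled patients, Protocol 6.1.2 says: "They will not be considered for the primary endpoint of the trial". The denominator can therefore differ from 31 or 33, and the critical count changes with it.

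**The case against.** The strongest defence is the reversed margin. Tested against 20% and 8%, exact power is 96% at 31 and 80% at 33, so both enrolled sizes reach the target. At the stated evaluable sizes it gives 96% at 28 and 72% at 30. Treating the margin as extra effect (true rates 60% and 28%) gives 95% at 28 and 63% at 30. The reversed reading would count cohort 4 a success against 8%, below the plan's own 13% reference, which is not superiority. It does not rescue the claim.

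Four further points are fair and should temper how the result is quoted.

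- **Formula.** The R function's form is an assumption, and the choice of variance moves 155 and 438 to 130 and 280. Every such figure is still far above 28 and 30, and Step 2 does not use the formula.
- **Discreteness.** Exact power rises and falls with n, and 31 and 33 happen to be low points: 30 gives 70.8% against 30%, and 32 gives 46.1% against 13%. Over 30 to 33 patients the chance of missing in cohort 4 is 54-66% (null 13%) or 82-88% (null 18%).
- **Size of the gap.** Against 30% at the designed 28, the shortfall is moderate, 71% against 80%. The large gaps are in cohort 4 and under the nulls that include the margin.
- **Status of the trial.** It is labelled exploratory phase II, the SAP's primary tables show counts, percentages and confidence intervals, and there is no go/no-go rule. Even so, the plan states a specific power for a named test and links results to development decisions, so the figure should be right.

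**Conclusion.** The concern holds. The 80% claim is wrong under both nulls that fit a superiority test, at the evaluable sizes and at the enrolled sizes. If the expected rate is true, the chance of a non-significant result in cohorts 1-3 is 29% at 28 and 36% at 31 (null 30%), or 71% and 76% (null 40%). In cohort 4 it is 62% at 30 and 66% at 33 (null 13%), or 87% and 88% (null 18%). Cohort 4 is not powered for a 10-point gain on either reading. These figures assume an exact one-sided 5% binomial test on complete data. The success threshold is also open: 15 or 18 of 31, and 9 or 11 of 33, depending on a null that nobody has written down.

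**What to change.** Keep the enrolled numbers and change the text in Protocol 11.3, the synopsis, and SAP 3.6 and 3.7.3.

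1. State for each cohort the single null proportion the binomial test uses and whether it includes the margin. The choice is the sponsor's. Protocol 13.6 lists the last patient in at December 2019, so nine-month outcomes fall around September 2020, before this June 2021 edition. If outcomes were known when the null was chosen, label it post hoc.
2. Define success as a rule, not a fixed count: exact one-sided 5% binomial test against that null at the number actually analysed. It would help to add how the multiply imputed data sets of SAP 3.7.5 are combined into one decision.
3. Withdraw the 80% claim and report attained size and power for the chosen null, ideally across 28-31 and 30-33. With 30% and 13%: size 2.4% and power 64% at 31, size 2.2% and power 34% at 33, and 80% power only at true rates near 54% and 33%. With 40% and 18%: power about 24% and 12%.
4. Say plainly that cohort 4 is not powered for a 10-point gain.

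No patients are added and no clinical procedure changes. The cost is a less favourable power statement and, possibly, a null that has to be called post hoc.
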